	
Phase II - Pharmacokinetic sub-study
 
◦ C_{max}: maximum concentration.◦ t_{max}: time to maximum concentration.◦ AUC_{0-t_0-t}: area under concentration-time curve, from 0 to the last blood sampling time point with measurable concentration.◦ $t_{1/2}$: elimination half-life. 
Phase III - Non-inferiority
 
• Primary efficacy endpoint: proportion of patients with adequate bowel cleansing: BBPS total score ≥ 6, with a score for each of the three colon segments (right; transverse, including flexures; and left, including sigmoid and rectum) ≥ 2 during colonoscopy after standard washing and air insufflation for luminal distension.• Secondary efficacy endpoints
◦ Number, appearance, size, location and histological classification of neoplastic and inflammatory colorectal lesions detected.◦ Adenoma detection rate, defined as the percentage of patients with at least one adenoma detected.◦ Caecal intubation rate, defined as the percentage of patients with appendiceal orifice visible to the endoscopist.◦ Ottawa Scale for bowel cleansing evaluation before washing and air insufflation for luminal distension.• Safety and tolerability
◦ Proportion of patients in safe conditions, defined as the absence in each colon segment (right, between ileocecal valve and appendix or as close as possible to the ileocecal valve in case of obstacles that prevent reaching the valve; transverse, including flexures; and left at the sigmoidal-rectum junction, 15-25 cm from anal margin) of potentially dangerous levels of H_2 and/or CH_4 ($>4\% Vol$ and $>100\% LEL$, respectively) during colonoscopy after standard washing and air insufflation for luminal distension.◦ Incidence of adverse events from the beginning of study drug self-administration.◦ Proportion of patients with change from baseline considered clinically significant by the Investigator of haematological and chemical parameters 4 hours and 8 hours after completion of study drug self-administration.◦ Proportion of patients with change from baseline considered clinically significant by the Investigator of vital signs (heart rate, systolic and diastolic blood pressure) measured during visits, as well as clinically significant change of pulse oximetry and heart rate measured during colonoscopy and systolic and diastolic blood pressure measured immediately prior and after colonoscopy. Of note, clinically significant changes of systolic and diastolic blood pressure measured during colonoscopy will also be reported if considered clinically significant by the Investigator. 
Of note, a clinically significant change of a given parameter is defined as a change that causes an additional control or a medical intervention.
 
• Adherence and acceptability
◦ Adherence: study drug completely taken, partially taken, not taken.◦ Bowel Cleansing Impact Review (BOCLIR) (only at Italian centres).◦ Ease of use: NRS (0=very difficult to 10=very easy).

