To define the pharmacokinetic profile of the mannitol doses used in dose finding through a pharmacokinetic sub-study.	
Adherence and acceptability
 
 • Adherence: study drug completely taken, partially taken, not taken • Ease of use: numeric rating scale (NRS) (0 = very difficult to 10 = very easy) • Taste: NRS (0 = terrible to 10 = very good) • Willingness to reuse the preparation (yes/no) 
• C_{max}: maximum concentration
 
• t_{max}: time to maximum concentration
 
• $AUC_{0-t_{0-}}$: area under concentration-time curve, from 0 to the last blood sampling time point with measurable concentration
 
• $t_{1/2}$: elimination half-life

Phase III - Non-Inferiority	
Objectives	Endpoints
To demonstrate the non-inferiority of mannitol vs. standard split 2L PEG ASC (Moviprep®) in bowel cleansing for colonoscopy.	
Primary Efficacy endpoint
 
 • Proportion of patients with adequate bowel cleansing, defined as BBPS total score ≥ 6, with a score for each of the three colon segments (right; transverse, including flexures; and left, including sigmoid and rectum) ≥ 2 during colonoscopy after standard washing and air insufflation for luminal distension. 
Secondary efficacy endpoints
 
 • Number, appearance, size, location and histological classification of neoplastic and inflammatory colorectal lesions detected. • Adenoma detection rate, defined as the percentage of patients with at least one lesion detected. • Caecal intubation rate, defined as the percentage of patients with appendiceal orifice visible to the endoscopist. • Ottawa Scale for bowel preparation before washing and air insufflation for luminal distension.
To assess the safety and tolerability of mannitol.	
 • Proportion of patients in safe conditions, defined as the absence in each colon segment (right, between ileocecal valve and appendix or as close as possible to the ileocecal valve in case of obstacles that

[figure not shown]
Phase III - Non-Inferiority	
Objectives	Endpoints

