8.1.3 PHASE III

The following assessments will be performed during phase III of the study:

- Informed consent, demographic features (age, sex and ethnicity), medical history and indication for colonoscopy are collected at Visit 1.
- Fulfilment of inclusion/exclusion criteria is definitively assessed at Visit 3.
- Evaluation of bowel preparation – Boston Bowel Preparation Scale (BBPS)

The BBPS is to be completed at Visit 4 after standard washing and air insufflation for luminal distension. See [Section 8.1.1](#) for scoring details and [Appendix 2](#) for a visual representation of BBPS scoring

- Evaluation of bowel preparation – Ottawa Scale (OS)

The OS total score ranges from 0 to 14 and is calculated by adding up the scores for each of the three segments of the colon (right, middle, left including sigmoid and rectum), each receiving a score on a 5-point scale (0-4), where 0 = perfect preparation, 1 = presence of clear liquid that does not require suction, 2 = presence of liquid that must be suctioned, 3 = presence of stool that must be flushed, 4 = presence of not-washable stool plus the overall amount of colonic fluid graded using a 3-point scale (0-2). Adequate preparation = OS < 6 (*Rostom et al., 2004*). The evaluation is performed at Visit 4 before washing and air insufflation for luminal distension. See [Appendix 3](#) for a visual representation of Ottawa Scale scoring.

- Colorectal lesions

The following features of colorectal lesions detected during colonoscopy at Visit 4 are to be recorded on the eCRF:

- Number
- Appearance (pedunculated, not pedunculated)
- Size (<5 mm, 5-9 mm, 10-19 mm, ≥ 20 mm)
- Location (right; transverse, including flexures; and left, including sigmoid and rectum)
- Histological classification (hyperplastic; inflammatory; tubular adenoma with low grade (LG) dysplasia <10 mm or ≥ 10 mm; tubular adenoma with high grade (HG) dysplasia <10 mm or ≥ 10 mm; adenoma with villous component >20% with LG or HG dysplasia; sessile serrated adenoma; adenoma; advanced adenoma; invasive cancer)
- Confirmation of caecal intubation, defined as identification of the appendiceal orifice.
- Measurement of intestinal gas concentrations

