Descriptive statistics and Wald 95% CIs of the following adherence and acceptability variables will be provided for each dose:

- Adherence
- NRS score for ease of use and taste
- Willingness to reuse the preparation

Phase II - Pharmacokinetic sub-study

The pharmacokinetic parameters (C_{max} , t_{max} , AUC_{0-t} , $t_{1/2}$) of each dose will be analysed descriptively on the PK population.

Phase III - Non-inferiority

Primary efficacy analysis

The proportion of patients with adequate bowel cleansing (BBPS total score ≥ 6 , score ≥ 2 for each segment) during colonoscopy after standard washing and air insufflation for luminal distension will be calculated to evaluate the non-inferiority of the test drug vs the standard drug.

Non-inferiority will be assessed by computing the two-tailed Wald 95% confidence interval (CI) of the difference between the two proportions $\pi_T - \pi_S$. Non-inferiority is met if the 95% CI does not cross the predefined non-inferiority margin $\Delta = -0.08$ and lies entirely to the right of the margin (i.e. non-inferiority will be demonstrated if the lower bound of the two-sided 95% CI of the difference is > -0.08).

The non-inferiority margin $\pi_T - \pi_S = -0.08$ corresponds to a relative risk $\pi_T/\pi_S = 0.906$ when the proportion of successes in the standard group is 0.85. Should the proportion of successes in the standard group be lower than 0.85, the non-inferiority margin will be adjusted in order to have a relative risk of at least 0.906 (e.g. if the proportion of successes observed in the standard group is 0.80, the non-inferiority margin $\pi_T - \pi_S$ will be set equal to $= -0.075$, corresponding to a relative risk equal to 0.906).

If the 95% CI of the difference lies completely to the right of 0, the test treatment can be considered superior to the standard treatment at a 5% significance level.

The Wald method for non-inferiority of proportions will be applied (*Dann RS, 2008*).

The analysis will be performed on both the FAS and PP populations. Results from both populations will have equal importance.

Secondary efficacy analyses

The analysis of secondary variables will be performed on the FAS. No between-group inferential analysis will be performed. Descriptive statistics and 95% CIs of the between-group differences will be applied on the following variables:

- Number, appearance, size, location and histological classification of neoplastic and inflammatory colorectal lesions detected

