- Adenoma detection rate
- Caecal intubation rate
- Ottawa bowel preparation scale

Confidence intervals for proportions will be calculated based on the Wald method.

Adherence and acceptability

The analysis of adherence variables will be performed on the FAS. No between-group inferential analysis will be performed. Descriptive statistics and Wald 95% CIs of the between-group differences will be applied on the following variables:

- Bowel Cleansing Impact review (BOCLIR) scales
- Adherence
- NRS score for ease of use and taste
- Willingness to reuse the preparation

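### Section 3 defines the adenoma detection rate by any lesion, contradicting the synopsis and counting patients without an adenoma as adenoma-positive

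*Combined protocol and SAP*

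**What the plan says.** The adenoma detection rate is a Phase III secondary efficacy endpoint and is defined twice in the current text.

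- Section 1.1 (synopsis): "Adenoma detection rate, defined as the percentage of patients with at least one adenoma detected".
- Section 3 (objectives and endpoints): "Adenoma detection rate, defined as the percentage of patients with at least one lesion detected".

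The Section 3 bullet just above the definition is a separate endpoint on lesion characteristics: "Number, appearance, size, location and histological classification of neoplastic and inflammatory colorectal lesions detected". Section 8.1.3 sets out what is recorded for each lesion. Its histology list begins "Histological classification (hyperplastic; inflammatory; tubular adenoma with low grade (LG) dysplasia" and ends "sessile serrated adenoma; adenoma; advanced adenoma; invasive cancer".

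Section 9.4.1 lists "Adenoma detection rate" among the secondary variables with no definition. On how these variables are analysed it says "The analysis of secondary variables will be performed on the FAS" and "No between-group inferential analysis will be performed". Descriptive statistics and 95% confidence intervals for the between-group differences are planned.

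**The concern.** One named endpoint has two numerators, and the analysis section does not say which governs. A programmer who works from Section 3 would count every patient with any recorded lesion and label the result an adenoma detection rate.

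Two things are at stake. The rate in each arm would be overstated, so it could not be compared with adenoma detection rates reported elsewhere. The between-arm difference, which is the quantity given a confidence interval, would also depend on lesions that are not adenomas: these can dilute a real difference or produce one where none exists. The protocol's own rationale in Section 2.1 ties cleansing quality to neoplasia detection and missed adenomas, so this is the secondary endpoint closest to that argument. If both definitions stand until the data are seen, either version could be reported as planned.

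**Working it through.** **Plan's own figure.** There is none to reproduce. The documents give no expected adenoma detection rate, lesion rate or power for this endpoint. The Phase III sample size (313 per group, raised to 348) rests on the primary endpoint and does not depend on this definition.

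**Does lesion mean something wider than adenoma here?** Section 8.1.3 lists hyperplastic, inflammatory and invasive cancer as histology categories separate from the adenoma entries. The two definitions then classify patients as follows.

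| Patient's recorded lesions | Section 3 | Synopsis |
|---|---|---|
| At least one adenoma, with or without others | positive | positive |
| Hyperplastic only | positive | negative |
| Inflammatory only | positive | negative |
| Invasive cancer only | positive | negative |
| None | negative | negative |

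Every adenoma is a lesion, so in each arm:

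Section 3 rate = adenoma rate + share of patients whose only lesions are not adenomas.

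The Section 3 rate therefore equals or exceeds the adenoma rate. That direction needs no assumption; the size does.

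**Size of the excess, first illustration.** Section 2.1 quotes polyp detection of 24.6% with good or excellent preparation, from a randomized comparison of PEG regimens. Take this as a stand-in for the lesion rate, and assume (not from the documents) that a fraction f of lesion-positive patients, 20% to 50%, have no adenoma. Adenoma rate = 24.6% × (1 − f):

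- f = 0.20: 24.6% × 0.80 = 19.7%, an excess of 4.9 points (ratio 1/0.80 = 1.25).
- f = 0.50: 24.6% × 0.50 = 12.3%, an excess of 12.3 points (ratio 1/0.50 = 2).

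The 24.6% applies to well-prepared patients only; the same source gives 12.2% for fair or poor preparation. Weighting by the protocol's expected 85% adequate cleansing, and equating adequate with good or excellent, gives 0.85 × 24.6% + 0.15 × 12.2% = 22.7%. The excess is then 4.5 to 11.4 points, much the same.

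**Size of the excess, second illustration.** With 348 patients per arm, assumed shares of 5%, 10% and 20% of all patients having only non-adenoma lesions add 348 × 0.05 = 17, 348 × 0.10 = 35 and 348 × 0.20 = 70 falsely positive patients per arm.

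**Effect on the difference (assumed figures).**

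- Masking: let the true adenoma rates be 30% and 25%, and let a share s of adenoma-negative patients in both arms have some other lesion. The Section 3 difference is (30% − 25%) × (1 − s), which is 4.5, 4.0 and 3.5 points for s = 10%, 20% and 30%, against a true 5.0.
- Creation: let the true adenoma rates be equal, with patients having only non-adenoma lesions making up 10% of one arm and 5% of the other. The Section 3 difference is 10% − 5% = 5 points, against a true 0.

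For scale, with an adenoma rate of 25% in both arms, the 95% half-width for the difference is 1.96 × √(2 × 0.25 × 0.75 / 348) = 6.4 points. A 5-point artefact is nearly that large.

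**The case against.** The strongest reply is that this is a one-word slip whose intended meaning is plain. The endpoint's name says adenoma, the synopsis defines it that way, lesion counts and histology are already a separate endpoint, and nothing in the documents ranks Section 3 above the synopsis. The consequence is also limited. The endpoint is secondary, analysed descriptively on the FAS without between-group inference, and plays no part in the primary test, the sample size or dose selection. Because histology is recorded, the adenoma-based rate can be derived whichever wording is read. The numerical illustration rests on an assumed share and on a polyp rate from one cited study's well-prepared subgroup.

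Most of this stands, and it limits the weight of the point. Section 3 is probably a slip, no data are lost, and the magnitude is illustrative only. What does not follow is that the text can be left alone. Section 3 states an explicit rule that gives the wrong number if followed, and no passage says that the synopsis overrides it. Descriptive status does not protect an estimate and its confidence interval from a mislabelled numerator.

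**Conclusion.** The concern holds. The two definitions conflict, and the Section 3 version does not measure what the endpoint's name says. Under it, the reported rate exceeds the adenoma detection rate by the share of patients with only hyperplastic, inflammatory or invasive cancer findings. The documents do not give that share. With 20% to 50% of lesion-positive patients assumed to have no adenoma and a 24.6% lesion rate, the excess is about 5 to 12 points. The direction of the error is certain, its size is not, and the difference between arms can move either way. The primary non-inferiority conclusion and the sample size are unaffected. This should be corrected before the secondary analyses are programmed.

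**What to change.** In Section 3, replace the reference to any lesion with at least one adenoma, matching the synopsis. Repeat that definition in Section 9.4.1, where the endpoint is now only named.

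Two details are worth settling in the same edit. First, state that the adenoma must be histologically confirmed; the synopsis does not say so, so this is an addition to its wording. Second, list which Section 8.1.3 categories qualify, and in particular whether sessile serrated adenoma counts, since matching the synopsis alone would leave that open. If a rate of patients with any lesion is also wanted, report it separately as a lesion (or polyp) detection rate.

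The cost is a phrase in Section 3 and a sentence or two in Section 9.4.1. No new data are needed, because histology is already collected, and no sample size changes.

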4 STUDY DESIGN

4.1 OVERALL DESIGN

This is a phase II/III, international, multicentre, randomized, parallel-group, endoscopist-blinded study that combines a phase II dose-finding study/pharmacokinetic sub-study with a phase III non-inferiority efficacy study (see [Figure 4-1](#)). The population for phase III will not include the patients who participated in phase II.

Figure 4-1 Study design

In both phases, the study drugs will not be blinded, but all endoscopists performing study colonoscopies will not be aware of group allocation; patients and site personnel involved in the randomization of the patient and management of the study drugs will be instructed not to disclose group allocation to the endoscopists. Experienced endoscopists will undergo specific training to decrease inter-observer variability in the evaluation of bowel cleansing and to refine intestinal gas measurement techniques.

Details of all the assessments to be performed are available in the schedule of activities (SoA) in [Section 1.2](#) and in [Section 8](#).

4.1.1 PHASE II

The parallel-group dose-finding phase will be conducted at approximately 8 centres and will involve 150 patients randomly assigned (1:1:1 ratio) to one of the following three treatment groups:

- 50 g mannitol powder to be dissolved in 500 ml of water
- 100 g mannitol powder to be dissolved in 750 ml of water
- 150 g mannitol powder to be dissolved in 1000 ml of water

Of note, these doses of mannitol have been selected as this range includes the minimum (50 g) and maximum (150 g) mannitol doses used effectively in the proposed indication, as reported in published literature. Please refer to [Section 2.1](#) for further details.

Randomization is stratified by centre and by the presence of constipation (yes/no), defined as the recurrent use of laxatives or Bristol Stool Form Scale (BSFS) < 3 in the two weeks prior to randomisation.

To limit patient exposure to an ineffective dose causing repetition of colonoscopy, the adequacy of bowel cleansing will be monitored continuously and enrolment in a treatment group will be discontinued as soon as 25% of treated patients present inadequate bowel cleansing causing repetition of colonoscopy. The stopping rule, mainly guided by clinical considerations, will be applied in each treatment group as follows:

- Up to the 25th enrolled patient, enrolment in a treatment group will be stopped as soon as 6 patients present inadequate bowel cleansing causing repetition of colonoscopy (i.e. if among the initial 15 patients enrolled in a treatment group, 6 need to repeat the cleansing procedure, the treatment group will be immediately discontinued).
- From the 26th enrolled patient on (if treatment was not discontinued earlier), enrolment will be stopped as soon as 25% of patients present inadequate bowel cleansing causing repetition of colonoscopy (i.e. if among the initial 32 patients enrolled in a treatment group, 8 need to repeat the cleansing procedure, the treatment group will be immediately discontinued).

The appropriate mannitol dose to be used in the comparative non-inferiority phase (phase III) will be singled out at the end of dose-finding based on the following criteria:

- 75% or greater rate of adequate bowel cleansing.
- Rate of patients in safe conditions, defined as absence of potentially dangerous levels of H₂ and CH₄ in each colon segment (right, between ileocecal valve and appendix or as close as possible to the ileocecal valve in case of obstacles that prevent reaching the valve; transverse, including flexures; and left at the sigmoidal-rectum junction, 15-25 cm from anal margin) after standard washing and air insufflation for luminal distension).
- Clinical judgment based on the caecal intubation rate, the incidence of adverse events, treatment adherence and acceptability (considering ease of use, taste and willingness to reuse the preparation).

Should two or all three doses prove to be equally safe and effective, the lowest dose will be selected for phase III of the study.

Study visits

Phase II of the study consist of four visits:

Visit 1 (≤ 28 days before the day of colonoscopy): after signed written informed consent is obtained, information concerning demographics, medical history, concomitant medications and indications for colonoscopy will be collected in the electronic case report form (eCRF). The incidence of adverse events will be recorded.

Visit 2 (≤ 7 days before the day of colonoscopy): to complete the verification of inclusion/exclusion criteria, a blood sample will be drawn to assess the haematological and chemical parameters (including electrolyte levels) of all patients and to perform a pregnancy test for women of childbearing potential. Assessments include a urinalysis and the measurement of vital signs (blood pressure and heart rate). The incidence of adverse events will be recorded.

Visit 3 (≤ 7 days before the day of colonoscopy): if inclusion/exclusion criteria are met, the Bristol Stool Form Scale (BSFS) will be administered, randomization will be performed, study drug will be dispensed and verbal and written instructions for its use will be provided. The date and time of colonoscopy will be communicated and reported on a form given to the patient. On the same form, patients will indicate date and time of start and end of study drug self-administration. The incidence of adverse events will be recorded.

More than one visit may take place on the same day.

Visit 4 (day of colonoscopy):

A blood and urine sample will be collected at the following time points:

- 4 hours ± 30 minutes after the end of study drug self-administration
- 8 hours ± 30 minutes after the end of study drug self-administration

After completion of bowel preparation, prior to colonoscopy, patients will fill in the questionnaire on acceptability and adherence.

The blinded endoscopist will then perform the scheduled colonoscopy using a standard colonoscope recording data on bowel cleansing using the BBPS and measuring intestinal gas concentrations in each colon segment after standard washing and air insufflation. Of note, CO₂ insufflation and water-aided techniques for colon distension (e.g. water immersion, water exchange) will not be allowed. The endoscopist will also confirm caecal intubation, defined as identification of the appendiceal orifice. Drugs administered for the procedure will be recorded.

Intestinal gas (H₂, CH₄ and O₂) concentrations in each segment will be measured using a multi-gas detector (Dräger X-am® 8000). Further information is available in the *Gas Detector Technical Documentation*. Use of any electrocautery device is allowed only during withdrawal and after washing and air insufflation. If H₂ and/or CH₄ levels are potentially dangerous, any electrosurgical procedure must be avoided.

Vital signs (heart rate and blood pressure) will be measured prior to colonoscopy. Oxygen saturation and heart rate will be measured continuously during colonoscopy, but only clinically significant abnormal findings will be recorded on the eCRF, where clinically significant means that these abnormal findings cause an additional control or a medical intervention.

The incidence of adverse events will be recorded.

